### 9.2. Clinical Laboratory Assessments

Clinical laboratory assessments including coagulation, platelet function test, hematology, clinical chemistry, and urinalyses will be summarized for each visit. In addition, changes from the baseline visit will be calculated for each visit if baseline and post-baseline measurements are available.

Shift tables will also be used to display the change from before treatment to after treatment measurement with respect to reference ranges “missing”, “low”, “normal”, “high”, and “total”.

To investigate whether platelet function test is prolonged when coadminstrated with LT3001 drug product, platelet function test observed under single treatment of aspirin, clopidogrel, apixaban or dabigatran will be summarized along with coadministration with LT3001 drug product. The number of subjects with Prolonged and Normal results will be summarized for COL/EPI and COL/ADP.

All laboratory evaluations, including those that are unscheduled, will be listed by subject. Out of range and clinically significant (CS) values will be flagged.

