#### Safety Review Schema

## Part B

Part B is open-label without placebo control. Approximately 48 subjects will be sequentially enrolled into four cohorts with 12 subjects in each cohort.

The first **3** subjects of each cohort will be “sentinel subjects”. After each sentinel subject completes the first day of combination treatments, the Investigator will review all available safety data from the sentinel subjects. If considered safe to do so, each sentinel subject will receive the remaining combination treatments.

The remaining combination treatments in a sentinel subject may not proceed in the event of any of the following:

- A subject experiences any severe hemorrhage which is assessed as related to the combination treatment
- A subject treated with LT3001 drug product experiences any SAE related to study drug (at least possibly related)
- Safety concerns per the Investigator’s clinical judgment

The dosing schema is summarized below.

Each Cohort of Part B	Sentinel Subjects	Remaining Subjects
Number of Subjects	3	9

In **Cohort 1**, each subject will receive a single 15-minute infusion of LT3001 [REDACTED] on Day 1. Each subject will receive multiple-dose aspirin as follows: a loading dose of 325 mg aspirin on the morning of Day 2 followed by a daily maintenance dose of 81 mg aspirin on Days 3 through 8 (Figure 2). The regimen is intended to achieve its maximal inhibitory effects on platelet function. Aspirin will be administered after breakfast. On the morning of Day 6, the dose of aspirin will be followed by the first dose of LT3001 0.025 mg/kg administered as a 15-minute IV infusion. Subjects will receive 9 doses of LT3001 on Days 6 through 8 (TID q3h). Each subject will be admitted into the study site on Day -1, stay until Day 8, and will have a follow-up visit on Day 15.

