#### 10.3.1. Safety Analyses

All safety analyses will be performed on the Safety Analysis Set. Adverse events will be coded by System Organ Class and Preferred Term using the latest version of MedDRA. Incidences of TEAEs (ie, events that started after exposure to study drug or worsened in severity after dosing) will be presented by dose group, maximum severity, and relationship to study medication.

Safety data will be summarized through appropriate data tabulations and standard descriptive statistics by treatment. For each continuous laboratory parameter, results will be categorized as low, normal, or high based on the laboratory normal ranges. Shift tables capturing the number and percentage of subjects shifting from these baseline to post-baseline categories will be presented.

The association of AEs, laboratory results, coagulation parameters, platelet function test, vital sign measurements, oximetry, and ECG results with the treatment of study drug or PK parameters may also be explored. If appropriate, statistical modeling will be performed to further characterize the associations mentioned above. All out-of-range and clinically significant laboratory results will be identified in subject data listings. The number and percentage of subjects in each dose group with normal and abnormal physical examination results will be presented for evaluations at baseline and final visit.

For each body system, changes in the subjects' findings from baseline to final visit (no change, normal to abnormal, or abnormal to normal) will be tabulated for each dose group.

To investigate whether platelet function test is prolonged when coadminstrated with LT3001 drug product, platelet function test observed under single treatment of aspirin, clopidogrel, apixaban or dabigatran will be compared with platelet function test observed under coadministration with LT3001 drug product. Platelet function test will be summarized with standard descriptive statistics by treatment. Shift tables capturing the number and percentage of subjects shifting from baseline to post-baseline categories will be presented.

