#### **4.1. Sample Size Justification**

Sample sizes were not based on statistical considerations. Sixteen subjects in Part A, and 12 subjects per cohort in Part B are deemed sufficient to achieve the study objectives.

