Discharge										X		
Prior and concomitant medication	X	X										
Adverse event										X		

ECG = electrocardiogram; ET = early termination; PK = pharmacokinetic

- a Virology tests will include HIV antibody, HBsAg, hepatitis C virus antibody, and COVID-19 antibody.
- b Demographics will include age, gender, height, body weight, body mass index (BMI) and race. On Day -1, only body weight will be measured.
- c Serum pregnancy test will be performed in female subjects of childbearing potential within 24 hours prior to the first drug treatment on Day 1.
- d Subjects will receive aspirin after breakfast. The dose of aspirin on Day 6, Day 7 and Day 8 will be followed immediately by 0.025 mg/kg LT3001 administered as a 15-minute IV infusion.
- e Physical examination will be performed at screening visit, predose on Day 1, the end of aspirin single treatment on Day 5, the end of combination treatment on Day 8 and follow-up visit on Day 15.
- f Vital signs will include body temperature, blood pressure, respiratory rate, and heart rate. Measurements will be made after the subject has rested in a supine position for at least 3 minutes. Blood pressure will be assessed in seated and supine position at predose and 60 minutes after dosing/infusion, only supine position at 20 minutes after dosing/infusion. Vital signs will be assessed at screening visit, Day 1 to 5 (pre-dose), Day 6 to Day 8 (each LT3001 dosing period at pre-dose, 20 minutes and 60 minutes after infusion is initiated), and follow-up visit on Day 15.
- g A 12-lead ECG assessment will be performed at screening visit and at pre-dose and 1 hour after taking aspirin on Day 2 to Day 5, one hour after the infusion is initiated of the first dose of LT3001 on Day 6 to Day 8 and follow-up visit on Day 15.
- h PK blood samples of LT3001 will be taken at 30±1, 45±1, and 60±5 minutes after infusion is initiated (end of infusion).
- i PK blood samples of LT3001 will be taken at 30±1, 45±1, and 60±5 minutes after infusion is initiated (end of infusion).
- j PK blood samples of aspirin will be taken at 30±1, 45±1, and 60±5 minutes after postdose.
- k Platelet function test and coagulation test will be measured at pre-dose on Day -1 and at 15 min and 6 hour 15 min after the last dose of aspirin single treatment on Day 5.

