## 6. GENERAL ASPECTS OF THE STATISTICAL ANALYSIS

### 6.1. Key Definitions

The Study Day is the day relative to the first day of study drug administration (Day 1).

Unless otherwise specified, Baseline is the last non-missing observation before the administration of any study treatment.

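### For Part B platelet function, SAP 9.2 plans no within-subject difference (combination minus partner drug alone) with an interval; the only output it names for that question is counts of Prolonged and Normal

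*SAP*

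**What the plan says.** - **Protocol 10.3.1.** To learn whether LT3001 prolongs the platelet function test, "platelet function test observed under single treatment of aspirin, clopidogrel, apixaban or dabigatran will be compared with platelet function test observed under coadministration" with LT3001. The protocol adds descriptive statistics by treatment and shift tables.
- **SAP 9.2.** It keeps the same question but says the two conditions will be summarised together rather than compared. The output named for that question is: "The number of subjects with Prolonged and Normal results will be summarized for COL/EPI and COL/ADP". SAP section 2 gives the SAP's methods precedence over the protocol's.
- **Other laboratory output in SAP 9.2.** Platelet function and coagulation are summarised at each visit, with changes from baseline, shift tables and a listing of every value by subject. The continuous statistics in SAP 10.1 include no confidence interval.
- **Baseline, SAP 6.1.** "Baseline is the last non-missing observation before the administration of any study treatment".
- **Schedule, SAP 4.2, Part B Cohort 1.** Partner-alone tests are taken "at 15 min and 6 hour 15 min after the last dose of aspirin single treatment on Day 5". Combination tests are taken at the end of the first LT3001 infusion on Day 6 and of the last on Day 8. The other cohorts follow the same pattern.
- **Protocol 5.1, on the Cohort 1 aspirin regimen.** "The regimen is intended to achieve its maximal inhibitory effects on platelet function".

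**The concern.** The Part B question is what LT3001 adds to an antiplatelet or anticoagulant drug already on board. The partner-alone result in the same subject isolates that addition. The planned change scores instead start from a drug-free value, so at a combination visit they contain the partner's effect plus any LT3001 effect. Counts split at a threshold have a different weakness: once a subject is Prolonged on the partner, any further lengthening leaves the count unchanged.

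At stake is a platelet function endpoint that Protocol section 4 lists as primary for Part B. For pharmacokinetics, SAP 8.3 gives every cohort a mixed model with subject as a random effect and a 90% CI for the with/without contrast. The bleeding-related interaction gets no such contrast.

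**Working it through.** The plan states no effect size, SD or precision for this question, so there is no figure to reproduce. The only design input is the cohort size: "Sixteen subjects in Part A, and 12 subjects per cohort in Part B are deemed sufficient to achieve the study objectives".

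**1. Do the scheduled tests pair up?** In the protocol's schedule tables the last-day infusions fall at hours 169, 172 and 175 (Cohort 1), 193, 196 and 199 (Cohort 2), and 145, 148 and 151 (Cohorts 3 and 4). The third infusion therefore starts 6 h after the first (175 − 169 = 199 − 193 = 151 − 145 = 6). The first infusion of the day immediately follows the partner dose, so a test 15 min into the third infusion is about 6 h 15 min after that dose.

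| Cohort | Partner alone | Combination | Match |
|---|---|---|---|
| 1 | Day 5: 15 min, 6 h 15 min | Day 6: 15 min; Day 8: about 6 h 15 min | time after dose |
| 2 | Day 6: 15 min, 6 h 15 min | Day 7: 15 min; Day 9: about 6 h 15 min | time after dose |
| 3, 4 | Day 4, after the second daily dose: 15 min, 6 h 15 min | Day 5: 15 min; Day 7: about 6 h 15 min, both after the first daily dose | time after dose only; evening against morning dose |

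**2. What the planned tables give.** Let B be baseline, P partner alone and C combination. With the same subjects at each visit,

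mean(C − B) − mean(P − B) = mean(C − P).

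An invented 12-subject example gave 18.69 both ways. The point estimate can therefore be derived.

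**3. What they do not give.** The variance needed is

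Var(C − P) = Var(C − B) + Var(P − B) − 2 Cov(C − B, P − B).

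The covariance is not tabulated, and the raw visit SDs do not supply the covariance of C with P. In the same example the two change-score SDs were 34.91 and 16.32. Alone, they bound the paired SD only between 34.91 − 16.32 = 18.59 and 34.91 + 16.32 = 51.23; it was in fact 28.33.

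**4. Precision of the paired contrast.** With n = 12 complete pairs, the 90% half-width is t(0.95, 11)/√12 = 1.796/3.464 = 0.518 times the SD of the paired difference.

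If both visits have the same SD and within-subject correlation ρ (assumed; not in the documents), the half-width in visit-SD units is 0.518 × √(2(1 − ρ)):

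| ρ | Half-width |
|---|---|
| 0.3 | 0.613 |
| 0.5 | 0.518 |
| 0.7 | 0.402 |
| 0.9 | 0.232 |

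A reader who has only the tables and treats the visits as independent would get t(0.95, 22) × √(2/12) = 0.701.

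**5. Room left in the counts.** If a proportion p is Prolonged on the partner alone (assumed range), 12(1 − p) subjects on average can still move to Prolonged, and with independent subjects the chance that none can is p¹².

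| p | Can still move | Chance that none can |
|---|---|---|
| 50% | 6.0 | 0.0002 |
| 80% | 2.4 | 0.07 |
| 90% | 1.2 | 0.28 |
| 95% | 0.6 | 0.54 |

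**The case against.** **SAP 9.2 plans more than counts.** This stands. A reader might infer that added prolongation cannot be seen or estimated at all. The documents do not support that: by-visit summaries and changes yield the mean difference by subtraction, and the listings show each subject's values. What remains is that the estimate is indirect, needs complete subjects, and needs the 15 min and 6 h 15 min tests kept apart. The SAP does not say that they will be: SAP 6.2 uses visits as recorded on the eCRF. Working out an interval from the listings would be an unplanned analysis.

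**The protocol asks only for description, and its endpoint is change from baseline.** Also fair. Changes from Day -1 are the stated endpoint and must stay. Protocol 10.3.1 nevertheless plans a comparison with partner alone, and SAP 9.2 leaves the reader to make it. Table layouts are in a separate display document that is not available here.

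**This is a descriptive Phase 1 study.** SAP 6.3 plans no hypothesis test, and SAP 4.1 says: "Sample sizes were not based on statistical considerations". A power contest between counts and a paired test would therefore not describe this plan, and none is offered. An interval is not a test, and the SAP reports 90% intervals for pharmacokinetics under the same statement.

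**The ceiling is documented only for aspirin.** Correct. The documents give no Prolonged rate for any partner, and COL/EPI and COL/ADP are counted separately and may differ.

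**Coagulation goes beyond what the protocol asks.** Correct: Protocol 10.3.1 wants this comparison for platelet function only. A reader might also infer that coagulation changes in Part B mainly reflect the partner drug. The documents give no figures for that, and Protocol 3.2 describes aspirin and clopidogrel as antiplatelet agents.

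**Conclusion.** The point holds as a gap in precision and directness. For the platelet question, the governing text replaces a comparison with a joint summary, names only threshold counts, and takes changes and shifts from a drug-free reference. The mean added effect is obtainable only by subtraction; its within-subject SD and interval are not obtainable from the planned tables.

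The missing interval would have a 90% half-width of 0.518 times the SD of the paired difference with 12 complete pairs. This assumes that closure times are recorded as numbers, which the planned change scores imply, and that paired differences are roughly normal. How far the counts saturate depends on Prolonged rates that the documents do not give. The concern is best grounded in Cohort 1. In Cohorts 3 and 4 the contrast is less clean, because partner-alone and combination tests follow different daily doses. The change is worth making because it is cheap and uses data already scheduled.

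**What to change.** In SAP 9.2, for Part B:

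- Define the last partner-alone day as a second reference, alongside Day -1.
- For COL/EPI and COL/ADP closure time, report by cohort the within-subject difference (or geometric mean ratio), combination minus partner alone, with a 90% CI.
- Pair the 15 min partner-alone test with the end of the first infusion, and the 6 h 15 min test with the end of the last. Keep them as separate analysis visits.
- State that in Cohorts 3 and 4 the partner-alone tests follow the second daily dose and the combination tests the first, so only time after dose matches.
- Present the same contrast for PT, INR, aPTT and TT as supportive, since they are measured at the same times.
- Keep the counts, shift tables and Day -1 changes.
- If the platelet test has an upper reading limit, say how readings at the limit are handled; they would compress the difference.

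In the same edit, reconcile SAP 3.2, which lists bleeding time among the Part B endpoints where Protocol section 4 lists the platelet function test.

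The cost is SAP wording and a few extra tables. No new samples or visits are needed.

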### **9.3. Vital Signs**

Vital signs, including the assessments of systolic and diastolic blood pressure, heart rate, respiratory rate, and body temperature, will be summarized for each visit. In addition, changes from the baseline visit will be calculated for each visit.

All assessments, including those that are clinically significant (CS) or unscheduled, will be listed by subject.

### **9.4. ECG**

ECG parameters, including heart rate, PR interval, QRS interval, QT interval, and QTc interval, will be summarized for each ECG parameter and visit. In addition, changes from the baseline visit will be calculated for each visit.

All assessments will be listed by subject, and abnormal or clinically significant (CS) findings will be flagged.

### **9.5. Pulse Oximetry**

For Part A, pulse oximetry measurements will be summarized with descriptive statistics and listed by subject.

### **9.6. Physical Examination**

For each body system, the number and percentage of subjects with normal and abnormal results will be presented. Additionally, changes in the subjects' findings from baseline to final visit (no change, normal to abnormal, or abnormal to normal) will be tabulated.

All physical examination findings, including those that are unscheduled, will be listed by subject and clinically significant (CS) findings will be flagged.

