**Table 2 Schedule of Activities for Part B, Cohort 1**

Procedures	Screening Period		Treatment Period												Follow-up	ET s	
	Day -30 to -2	Day -1	Day 1	Day 2	Day 3	Day 4	Day 5	Day 6			Day 7			Day 8			
		Hour u	1	25	49	73	97	121	124	127	145	148	151	169	172	175	
Informed consent	X																
Urine drug/cotinine/alcohol test	X	X r															
Virology test a	X																
Demographics b	X	X															
Medical and surgical history	X																
Check In		X															
Serum pregnancy test c		X															
Aspirin d				X	X	X	X	X			X			X			
LT3001 drug product			X r					X	X	X	X	X	X	X	X		
Physical examination e	X		X				X								X	X	
Vital sign f	X	X	X	X	X	X	X	X	X	X	X	X	X	X	X	X	
12-lead ECG assessment g	X	X	X	X	X	X	X	X		X		X			X	X	
PK blood sample of LT3001																	
PK blood sample of Aspirin j																	
Platelet function test		X k					X k	X l						X m	X	X	
Coagulation n	X	X r					X k	X l						X m	X	X	
Hematology test o	X	X r					X							X	X	X	
Clinical chemistry test p	X	X r					X							X	X	X	
Urinalysis q	X	X r					X							X	X	X	
Discharge														X			
Prior and concomitant medication	X	X															
Adverse event														X			

ECG = electrocardiogram; ET = early termination; PK = pharmacokinetic

- a Virology tests will include HIV antibody, HBsAg, hepatitis C virus antibody, and COVID-19 antibody.
- b Demographics will include age, gender, height, body weight, body mass index (BMI) and race. On Day -1, only body weight will be measured.
- c Serum pregnancy test will be performed in female subjects of childbearing potential within 24 hours prior to the first drug treatment on Day 1.
- d Subjects will receive aspirin after breakfast. The dose of aspirin on Day 6, Day 7 and Day 8 will be followed immediately by [REDACTED] LT3001 administered as a 15-minute IV infusion.
- e Physical examination will be performed at screening visit, predose on Day 1, the end of aspirin single treatment on Day 5, the end of combination treatment on Day 8 and follow-up visit on Day 15.

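### Part B physical-examination change tables compare baseline only with the final visit, nominally 7 days after the last dose, so findings that arise during dosing and resolve are tabulated as no change

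*SAP*

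**What the plan says.** **Physical examination.** SAP 9.6 tabulates, for each body system, changes in subjects' "findings from baseline to final visit (no change, normal to abnormal, or abnormal to normal) will be tabulated". Protocol 10.3.1 plans the same change table. It also says that the number and percentage of subjects "with normal and abnormal physical examination results will be presented for evaluations at baseline and final visit". SAP 9.6 repeats those counts without naming a visit. It adds: "All physical examination findings, including those that are unscheduled, will be listed by subject".

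**When subjects are examined in Part B.** Footnote e of each Part B schedule (Protocol Section 2) gives screening, pre-dose on Day 1, and three later examinations. For Cohort 1 the later ones are "the end of aspirin single treatment on Day 5, the end of combination treatment on Day 8 and follow-up visit on Day 15". Cohorts 2 to 4 follow the same pattern on their own days.

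**Laboratory tests.** SAP 9.2 summarizes each laboratory group at each visit and says that "changes from the baseline visit will be calculated for each visit if baseline and post-baseline measurements are available". It then says: "Shift tables will also be used to display the change from before treatment to after treatment measurement with respect to reference ranges". Protocol 10.3.1 words the shift tables differently: "Shift tables capturing the number and percentage of subjects shifting from these baseline to post-baseline categories will be presented". SAP 2 lets the SAP's methods amend or supersede the protocol's.

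**The concern.** Both documents list change from baseline in physical examination among the primary Part B endpoints (Protocol 4, SAP 3.2). Part B has no placebo arm, so its most informative safety contrast is within subject: partner drug alone against partner drug plus LT3001. The schedules place an examination at the end of each of those two phases. The change table uses neither. It uses a visit about a week after dosing has stopped.

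Physical findings are recorded as normal or abnormal, so there is no numeric change at each visit to fall back on, as there is for laboratory values. A sign that appears under combination treatment and clears before follow-up leaves the subject in the no-change row.

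The laboratory shift table raises a smaller question. A shift table exists to count subjects who cross a reference limit. If the SAP does not say which later measurement is compared with baseline, one programmer could use follow-up and another the last on-treatment draw, and the two tables would answer different questions.

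**Working it through.** No power or sample-size figure is involved. The check is day arithmetic plus a comparison of the texts.

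**1. Interval from last dose to final visit in Part B** (days from Protocol 5.1 and footnote e of Tables 2 to 5; interval = follow-up day − last dosing day):

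| Cohort | End of partner alone | End of combination | Follow-up | Interval |
|---|---|---|---|---|
| 1 aspirin | Day 5 | Day 8 | Day 15 | 15 − 8 = 7 days |
| 2 clopidogrel | Day 6 | Day 9 | Day 16 | 16 − 9 = 7 days |
| 3 apixaban | Day 4 | Day 7 | Day 14 | 14 − 7 = 7 days |
| 4 dabigatran | Day 4 | Day 7 | Day 14 | 14 − 7 = 7 days |

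The Cohort 2 schedule prints a window of plus or minus 1 day at follow-up, so its interval runs from 15 − 9 = 6 to 17 − 9 = 8 days.

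**2. Examinations that reach the change table.** Each Part B subject has three scheduled examinations after dosing starts, and the change table uses one. Per cohort that is 12 × 3 = 36 scheduled examinations, with 12 × 1 = 12 used and 24 unused. Over 48 subjects it is 144 scheduled, 48 used and 96 unused.

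**3. What one subject looks like.** Take a Cohort 1 subject with a body system normal pre-dose on Day 1, normal on Day 5, abnormal on Day 8 and normal on Day 15.
- Change table as written (Day 1 against Day 15): no change.
- Change at each examination: Day 5 no change, Day 8 normal to abnormal, Day 15 no change.

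One such subject is 1/12 = 8.3% of the cohort at Day 8 and 0% in the table as written.

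**4. Laboratory data, SAP 9.2 against Protocol 10.3.1.**
- Numeric change from baseline is calculated at each visit, so the on-treatment draws are included.
- Platelet function has counts of prolonged and normal results under partner drug alone and under coadministration.
- The SAP shift table ends at an after-treatment measurement. SAP 6.1 defines baseline, but nothing defines that later measurement.
- The protocol's shift table runs to post-baseline categories generally. Neither document ties laboratory shifts to the follow-up visit.

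For laboratory data, then, the gap is an undefined term in one type of table.

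**5. Part A for comparison.** The final visit is at hour 73 and Dose 9 at hour 55, so the nominal gap is 73 − 55 = 18 hours. The long delay after dosing is a Part B feature.

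**The case against.** **What can be said for the plan.** No data are lost. Every examination finding is listed by subject, with clinically significant ones flagged. Protocol Appendix 4 counts an abnormal safety assessment judged clinically significant as an adverse event, and SAP 9.1 tabulates treatment-emergent events by term, severity and relationship. With 12 subjects per cohort a flagged listing can be read in full. SAP 9.6 names no visit for the normal/abnormal counts, so they may be produced at every visit. Table layouts are in a separate Data Displays Document that is not available here. No estimate, test or decision rule changes.

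All of this stands, and it limits the consequence. It does not change the comparison that both documents prescribe for the change table. A listing is not a summary, and the adverse-event route depends on the investigator's judgment of clinical significance.

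**Stronger readings that a reader might infer.**
- *That on-treatment laboratory abnormalities also appear in no shift or change table.* The documents do not support this. SAP 9.2 calculates change at each visit and counts prolonged platelet function under coadministration. Its after-treatment wording can be read as any measurement after dosing began.
- *That the categorical displays all look after the drug has gone and will show nothing whatever happened.* The platelet function counts contradict the first half. As to elimination, the documents give half-lives only for apixaban (up to 14 h) and dabigatran (up to 17 h): 168/14 = 12 and 168/17 = 9.9 half-lives. They give none for aspirin or clopidogrel. An eliminated drug also does not show that a physical sign has resolved; a sign still present at follow-up would be tabulated.

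**Conclusion.** The point stands for the Part B physical-examination change table. As written it uses one of three scheduled post-dose examinations, at a visit nominally 7 days after the last dose (6 to 8 in Cohort 2), and it reports a finding that arose and resolved in between as no change. This concerns a primary safety endpoint and should be corrected. The effect is on how safety is summarized: the underlying findings remain in listings and, where clinically significant, in the adverse-event tables.

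The laboratory part is secondary. One term in SAP 9.2 needs a definition so that category shifts during dosing are counted.

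Two assumptions apply. The final visit is taken to be the follow-up visit, which agrees with the completion definition in Protocol 5.2. The subject is taken to complete the cohort; for early termination the last examination could be nearer to dosing. How many findings would be missed cannot be estimated from the documents.

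**What to change.** **SAP 9.6.** State that normal/abnormal counts and change from baseline are tabulated, by body system and cohort, at each scheduled post-dose examination as well as the final visit. In Part B these are end of partner drug alone, end of combination treatment, and follow-up. Align the two final-visit sentences in Protocol 10.3.1. SAP 2 already gives the SAP's methods precedence, so the tables need not wait for that.

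**SAP 9.2.** Replace the undefined after-treatment measurement with a rule that matches the protocol's post-baseline wording: either shifts at each scheduled visit, or shifts to the worst post-dose category. If the worst category is used, say whether unscheduled results count, and present partner-alone and combination phases separately so that the within-subject contrast is visible.

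**Cost.** Wording changes and a few more tables, with no new data or visits. The tables will show more abnormalities, some of them transient and of no clinical importance, and the report will need to say so.
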